Protocol Study

Comparison of 3 direct laryngoscopes: Inscope DL blade size 3.5 and DL blade 3.5 Sun-Med GreenLine®/D™ to DL blade 3 SunMed GreenLine®/D™ for tracheal intubation in patients undergoing lumbar spine surgery, a prospective randomized study

11/06/2016

NCT02955511

Study Proposal

Comparison of 3 direct laryngoscopes: Inscope DL blade size 3.5 and DL blade 3.5 Sun-Med GreenLine®/D™ to DL blade 3 Sun-Med GreenLine®/D™ for tracheal intubation in patients undergoing lumbar spine surgery, a prospective randomized study

PRINCIPAL INVESTIGATOR

[name]., PhD., Program Director

CO-INVESTIGATORS

[name]
[name]
[name]
[name]
[name]
[name]

STUDY STAFF

INSTITUTION

Department of Anesthesiology
Cedars-Sinai Medical Center in Los Angeles
[name]
[name]

E-mail: [contact]

[contact]

[contact]

STUDY OBJECTIVES

Hypothesis

The use of Macintosh blade sized #3.5 (vs Macintosh size #3) would reduce the time required to achieve successful tracheal intubation and improve the glottic view.

Study objective

The purpose of this research study is to compare 3 different laryngoscope blades (sizes: 3.5, 3.5 and 3) and see if the blades size 3.5 will reduce the time required to achieve successful tracheal intubation and improve the physician's view of the glottis compared to the standard direct laryngoscope using the blade size 3, in patients undergoing lumbar surgery. The Sun-Med GreenLine®/D™ Macintosh Blade laryngoscope (size 3 and size 3.5) are already used at Cedars-Sinai Medical Center, but the Inscope Direct Laryngoscope (size 3.5) will be used at Cedars-Sinai Medical Center for the first time, as part of this research.

Primary end point: time to achieve successful tracheal intubation.

Secondary end points: glottic view at intubation, number of intubation attempts and effectiveness of the integrated suction in the Inscope Direct Laryngoscope.

BACKGROUND AND SIGNIFICANCE

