- (J) The attending will let the study coordinator know the POGO (Percentage Of Glottic Opening) and the best glottic view grade obtained using the POGO grading system (0% to 100%), and the Cormack Lehane scoring system (1/2/3/4).
- (K) If the intubation attempt is unsuccessful, time will be stopped when the anesthesiologist removes the intubating device from the mouth.
- (L) Rescue with bougie, Mac #4, fiberoptic bronchoscope, LMA, videolaryngoscope or any device necessary used by the attending anesthesiologist will be recorded. Should the need for an adjunct airway device be necessary for ventilation, any device can be used in accordance with the American Society of Anesthesiologist (ASA) difficult airway algorithm in case of a difficult airway.
- (M) If the anesthesiologist uses the suction, its time and frequency will be recorded.
- (N) Vital signs (MAP, heart rate, end-tidal CO2 and SpO2) obtained at standardized intervals before, during and after tracheal intubation will be recorded.

III Post-operative period:

A postoperative follow-up assessment will be performed approximately 4 hours after surgery by a co-investigator blinded to the intubation device to evaluate:

- 1. The presence and severity of sore throat,
- 2. Any changes in voice (e.g., hoarseness),
- 3. Trauma to the lip,
- 4. Trauma to the tongue,
- 5. Trauma to the gum, or
- 6. Trauma to the teeth.

II. Data Analysis:

The total study size is estimated to be 120 patients. A sample size of 40 patients in each group is determined by power analysis based on:

The primary and secondary hypotheses, namely the mean time required to complete the intubation process, for each of 2 DL groups compared with the control (standard DL) group and with each other (i.e., Group 1 vs. Group 2, Group 1 vs. Group 3, Group 2 vs. Group 3). In a single factor ANOVA study, sample sizes of 40, 40, and 40 are obtained from the 3 groups whose means are to be compared. The total sample of 120 subjects achieves 88% power to detect a difference of at least 10 seconds using the Tukey-Kramer (Pairwise) multiple comparison test at a 0.05 significance level. The common standard deviation within a group is assumed to be 8.60.

The following items will be analyzed:

- 1. Demographic information (weight, height, BMI, age, gender)

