- Airway evaluation: Mallampati class, mouth opening, presence or absence of teeth, gaps, thyro-mental distance, neck range of motion (Patients will be asked to move their neck in extension, flexion, rotation, and lateral binding)
- 3. Vital signs (MAP, heart rate, end-tidal CO2 and SpO2) obtained at standardized intervals before, during and after tracheal intubation
- 4. Type and amount of drugs administered during induction
- Assessment of the glottic view using the Cormack Lehane and POGO scoring systems at the time of tracheal intubation
- 6. Times from the passage of the blade between the teeth to obtain glottic view, to placement of the tracheal tube and the appearance of an end-tidal CO2 waveform
- 7. The number of intubation attempt(s) An intubation attempt was defined as the insertion of the laryngoscope blade in to the mouth of the patient, regardless of whether an attempt was made to insert a tracheal tube
- 8. The need to change to a different intubating device, and use of adjuvant airway device (eg, LMA, Bougie, fiberoptic bronchoscope, videolaryngoscope)
- 9. The use of suction and frequency
- 10. The presence and severity of trauma to the lip, tongue, gum, or teeth during intubation
- 11. The presence and severity of sore throat, any changes in voice, trauma to the lip, tongue, gum, or teeth in the recovery area
- 12. Blade Stained with Blood
- 13. Any complications

Definitions:

Intubation attempt: laryngoscope blade is inserted into the study participant. A failure will be recorded if the assigned laryngoscope is removed from the mouth to re-position twice.

Intubation Time: The time starts when the tip of laryngoscope blade passes the upper incisors and the time stops when the endotracheal tube is placed in the trachea, the cuff in inflate, and positive end-tidal CO2 detected.

Time to visualized vocal cords: The time starts when the tip of the video laryngoscope passes the upper incisors and the time stops when the provider has clearly visualized the vocal cords.

Ease of intubation: Immediately after the surgery, the performing anesthesiologist will be asked to judge the ease of intubation with each device on a scale from 1 to 4, where 1 = easy insertion without need of adjustment; 2 = need of one adjustment; 3 = two or more adjustments to obtain optimal visualization of the vocal cords, and 4 = impossible visualization and blind intubation or necessary use of an alternative airway device.

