## **Data Analysis:**

The total study size is estimated to be 120 patients. A sample size of 40 patients in each group is determined by power analysis based on:

The primary and secondary hypotheses, namely the mean time required to complete the intubation process, for each of 2 DL groups compared with the control (standard DL) group and with each other (i.e., Group 1 vs. Group 2, Group 1 vs. Group 3, Group 2 vs. Group 3). In a single factor ANOVA study, sample sizes of 40, 40, and 40 are obtained from the 3 groups whose means are to be compared. The total sample of 120 subjects achieves 88% power to detect a difference of at least 10 seconds using the Tukey-Kramer (Pairwise) multiple comparison test at a 0.05 significance level. The common standard deviation within a group is assumed to be 8.60.

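### Raw-mean ANOVA is the only primary analysis named: the stated inputs give about 99.7% power at 10 s, not 88%, but a small share of long times could erode it, and a log-scale analysis protects against that

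*SAP*

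**What the plan says.** The Protocol, under Study objective, sets "Primary end point: time to achieve successful tracheal intubation". The Data Analysis text, the same in Protocol and SAP, makes the quantity of interest a mean: "namely the mean time required to complete the intubation process", for all three pairs of blades. The design is a single-factor ANOVA in which "sample sizes of 40, 40, and 40 are obtained from the 3 groups whose means are to be compared". The power statement reads "The total sample of 120 subjects achieves 88% power to detect a difference of at least 10 seconds". The procedure behind that figure is described as "using the Tukey-Kramer (Pairwise) multiple comparison test at a 0.05 significance level". The spread is given without a source: "The common standard deviation within a group is assumed to be 8.60".

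Four other places bear on how long a recorded time can be:

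- **Definitions, Intubation Time (both documents).** The clock runs from the blade passing the incisors until the tube is in, the cuff is up and end-tidal CO2 is seen. There is no cap.
- **Protocol, Operative period, item (K).** After an unsuccessful attempt, timing stops when the device leaves the mouth. The text does not say whether the next attempt adds to that time, restarts it or replaces it.
- **Protocol, Operative period, item (L).** "Rescue with bougie, Mac #4, fiberoptic bronchoscope, LMA, videolaryngoscope or any device necessary used by the attending anesthesiologist will be recorded". Its effect on the primary time is not stated.
- **Definitions, Intubation attempt.** "A failure will be recorded if the assigned laryngoscope is removed from the mouth to re-position twice". No time value is attached to a failure.

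Neither document names a transformation, a rank-based test or a time-to-event method. Neither gives a rate or duration for repeat attempts or rescue.

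**The concern.** Intubation time is positive and has no upper limit as defined, and the plan provides for second insertions, failures and rescue devices. If those patients' times enter in full, one or two per arm can dominate the pooled variance of a raw-mean analysis. A real 10 s advantage of a 3.5 blade could then be missed because of a few long cases unrelated to that advantage, and the primary answer would depend on the arms in which they fell. The stated power gives no guide to how much of this the trial can absorb, because it does not follow from its own inputs and the SD cannot be traced.

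**Working it through.** **1. The plan's own figure.** Inputs from Data Analysis: n = 40 per arm, difference 10 s, SD 8.60, Tukey-Kramer at 0.05, error df = 120 − 3 = 117.

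- Critical |t| = q(0.95; 3, 117)/√2 = 2.374.
- SE of a pairwise difference = 8.60 × √(2/40) = 1.923 s.
- Noncentrality = 10/1.923 = 5.20.
- Power per pair (noncentral t) = **99.7%**, against 88% stated.

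Other readings do not recover 88%. An unadjusted t test gives 99.9%, Bonferroni 99.7%, and the overall F test 99.8% or more. Detecting all pairs that truly differ by at least 10 s gives about 99.5%. A figure of 88% would fit a difference of about 6.8 s at SD 8.60, an SD of about 12.6 s at 10 s, or about 20 patients per arm. The documents do not say which, if any, was meant.

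**2. How much spread the design tolerates.** Same formula, 10 s difference, 40 per arm:

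| SD (s) | 8.60 | 10 | 12 | 12.57 | 14 | 20 |
|---|---|---|---|---|---|---|
| Power per pair | 99.7% | 98.1% | 91.0% | 88% | 79.3% | 44.8% |

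The break-even SD is 12.57/8.60 = 1.46 times the planned one.

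**3. What would push the SD there.** Suppose a share p of every arm takes D extra seconds on top of a base SD of 8.60. Both p and D are assumptions. Then SD = √(8.60² + p(1−p)D²), and the D that brings the SD to 12.57 is √[(12.57² − 8.60²)/(p(1−p))].

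| p | SD at D = 60 s | Power at D = 60 s | D at which power reaches 88% |
|---|---|---|---|
| 2.5% (1 in 40) | √(73.96 + 87.75) = 12.7 | 87% | 58.7 s |
| 5% (2 in 40) | √(73.96 + 171) = 15.7 | about 68% | 42.1 s |
| 10% (4 in 40) | √(73.96 + 324) = 19.9 | 45% | 30.6 s |

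**4. Simulated power of three analyses.** Assumptions: lognormal times, control mean 30 s, both 3.5 arms 10 s faster, base SD 8.60, the same share of long cases in every arm, extra time uniform over the range shown.

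| Long cases | Raw Tukey | Log-scale Tukey | Steel-Dwass ranks |
|---|---|---|---|
| None | above 99% | above 99% | above 99% |
| 5%, 20-40 s extra | 95% | 99% | 99% |
| 5%, 30-90 s extra | 67% | 96% | 99% |
| 10%, 30-90 s extra | 43% | 86% | 97% |

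With 20-40 s extra, raw power is 98% at 2.5% long cases and 88% at 10%. Familywise error is 4-5% for all three methods. At a control mean of 40 s the raw and rank figures barely move. The log scale protects somewhat less: about 92% rather than 96% for 5% of patients with exactly 60 s extra.

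**5. The case that goes the other way.** Suppose the blades do not differ in typical time and the 3.5 arms only have fewer long cases (20% in control, 3% in the 3.5 arms, 30-90 s extra). Power is then about 51% raw, 38% log scale and 14% ranks.

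**The case against.** The strongest defence has four parts.

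- **The tail is not documented.** No rate or duration of long times is given, and 8.60 may already include some. A reader might infer that the real SD will be far above 8.60 and that power will be below 88%. The documents do not support that. The inputs leave a margin of about 12 points, and milder tails (20-40 s extra in 2.5-5% of patients) leave raw power at 95-98%. This stands, so the point is conditional.
- **Long times may never enter.** Item (K) stops the clock at blade removal. The Exclusion Criteria remove anticipated difficult intubation and a history of it, and operators must be experienced. This makes long times rarer or shorter. It does not rule out unanticipated ones, and the Intubation Time definition, read alone, counts them in full. The two texts leave the matter open.
- **The raw-mean test is valid and answers the stated question.** Type I error is held, and the hypothesis is about mean time. Both are true. The issue is loss of power and sensitivity to a few patients, not validity.
- **A robust test can discount what matters.** If a better blade helps by preventing long intubations, ranks lose most of the signal (14% against 51%). A reader might infer that a rank test should be the sole primary analysis. Step 5 argues against that. The log scale loses less (38%) and gains clearly when the whole distribution shifts.

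**Conclusion.** The concern holds in conditional form. Two parts rest on the documents alone. The stated 88% does not follow from the stated inputs, which give about 99.7% per pair. The only analysis named for the primary end point is a raw-mean comparison with an unsourced SD and no rule for repeat attempts, failure or rescue.

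The rest depends on assumptions. Power drops below 88% only if the SD exceeds about 12.6 s. Two patients in 40 per arm would be enough if each took about 42 s or more extra and that time counted in full. In the assumed range for 5% long cases, raw power runs from about 95% down to 67%, against 99% to 96% on the log scale. With no long cases nothing is lost by either choice.

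The mismatch between 99.7% and 88% should not be read as showing an underpowered trial. On its own inputs the trial has more power than it claims. The change is worth making because it is cheap protection, not because a loss has been shown.

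**What to change.** In the Data Analysis section of both Protocol and SAP:

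1. Make the primary analysis the same one-way ANOVA with Tukey-Kramer pairs at familywise 0.05, run on log(intubation time). Report geometric mean ratios with simultaneous 95% confidence intervals.
2. Keep the raw mean difference in seconds as a supportive analysis, and add Steel-Dwass with the Hodges-Lehmann difference as a sensitivity analysis.
3. Reconcile Operative period item (K) with the Intubation Time definition, so that it is clear before any data are seen how time over repeat attempts and rescue is counted. No analysis is well defined until this is done.
4. Give the source of the SD of 8.60 and correct or explain the 88%.

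**Cost:** wording and a few lines of code, with no change to sample size or data collection. The headline becomes a ratio rather than seconds. Power is also lower than for raw means if a blade helps only by reducing the number of long cases (about 38% against 51% in the scenario above). For that reason the mean difference and the number-of-attempts end point must be reported beside the primary result.

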## The following items will be analyzed:

- 1. Demographic information (weight, height, BMI, age, gender)
- Airway evaluation: Mallampati class, mouth opening, presence or absence of teeth, gaps, thyro-mental distance, neck range of motion (Patients will be asked to move their neck in extension, flexion, rotation, and lateral binding)
- 3. Vital signs (MAP, heart rate, end-tidal CO2 and SpO2) obtained at standardized intervals before, during and after tracheal intubation
- 4. Type and amount of drugs administered during induction
- 5. Assessment of the glottic view using the Cormack Lehane and POGO scoring systems at the time of tracheal intubation
- 6. Times from the passage of the blade between the teeth to obtain glottic view, to placement of the tracheal tube and the appearance of an end-tidal CO2 waveform
- 7. The number of intubation attempt(s) An intubation attempt was defined as the insertion of the laryngoscope blade in to the mouth of the patient, regardless of whether an attempt was made to insert a tracheal tube
- 8. The need to change to a different intubating device, and use of adjuvant airway device (eg, LMA, Bougie, fiberoptic bronchoscope, videolaryngoscope)
- 9. The use of suction and frequency
- 10. The presence and severity of trauma to the lip, tongue, gum, or teeth during intubation
- 11. The presence and severity of sore throat, any changes in voice, trauma to the lip, tongue, gum, or teeth in the recovery area

- 12. Blade Stained with Blood
- 13. Any complications

## **Definitions:**

Intubation attempt: laryngoscope blade is inserted into the study participant. A failure will be recorded if the assigned laryngoscope is removed from the mouth to re-position twice.

Intubation Time: The time starts when the tip of laryngoscope blade passes the upper incisors and the time stops when the endotracheal tube is placed in the trachea, the cuff in inflate, and positive end-tidal CO2 detected.

Time to visualized vocal cords: The time starts when the tip of the video laryngoscope passes the upper incisors, and the time stops when the provider has clearly visualized the vocal cords.

Ease of intubation: Immediately after the surgery, the performing anesthesiologist will be asked to judge the ease of intubation with each device on a scale from 1 to 4, where 1 = easy insertion without need of adjustment; 2 = need of one adjustment; 3 = two or more adjustments to obtain optimal visualization of the vocal cords, and 4 = impossible visualization and blind intubation or necessary use of an alternative airway device.

The provider will clear secretions as necessary to visualize and report the secretions encountered on a scale from 1 to 10, where 1 = no secretions and no visual obstruction 10=severe visual obstruction, unable to clear without removing device.

Postoperative evaluation: sore throat (0 = none and 10 = maximum discomfort), and whether they have postoperative dysphonia. Furthermore, the incidence of postoperative airway complications will be reported.
